9. STUDY POPULATION

Study population data will be summarised by, or under the direct auspices of Clinical Statistics GlaxoSmithKline.

The precise format and content of Study Population tables are shown in Section 15.1.1 of this RAP.

The study population tables will use the “All Subjects” population unless otherwise specified.

10. SAFETY ANALYSES

Safety analysis will be based on the All Subject Population. Safety parameters include adverse events, clinical laboratory evaluations, vital signs, ECGs, and physical examinations if data permit.

Clinical monitoring and laboratory safety will be reviewed by the Investigator but will not be formally analyzed. Vital signs and ECG data will be summarized by dose and time point.

The following safety data will be presented in tabular and/or graphical format and summarized descriptively according to GSK’s IDSL standards by, or under the direct auspices of Clinical Statistics, Quantitative Science, GSK.

PWH115760

- Exposure data
- Adverse events (AEs)
- Laboratory data, including hematology, clinical chemistry, routine urinalysis, lipase, amylase,
- Vital signs (systolic BP, diastolic BP, and pulse rate), weight/height
- ECG data

11. PHARMACOKINETIC ANALYSES

The reconciliation of the PK Case Report Form (CRF) and SMS2000 data will be performed by, or under the direct auspices of, Clinical Pharmacology Science and Study Operations (CPSSO), GlaxoSmithKline.

The merge of PK concentration data, randomisation and CRF data will be performed by, or under the direct auspices of, Clinical Statistics (programmer), GlaxoSmithKline.

Derivation of pharmacokinetic parameters will be performed by, or under the direct auspices of, Clinical Pharmacology Modelling and Simulation (CPMS), GlaxoSmithKline.

Statistical analysis of pharmacokinetic parameters will be performed by, or under the direct auspices of, Clinical Statistics (Statistician), GlaxoSmithKline.

Listings will be generated and summary statistics (n, arithmetic mean, standard deviation, minimum, median, maximum) will be calculated for each derived plasma pharmacokinetic (PK) parameter by regimen and time. PK parameters are listed in Section 2.1.1.

11.1. Drug Concentration Measures

Concentrations of GSK1278863 in plasma and its metabolites [M2, M3, M4, M5, M6 and M13] will be listed and summarised by treatment group and nominal time. Standard summary statistics will be calculated (i.e. mean and associated 95% confidence interval, standard deviation, median, minimum and maximum). Refer to the standard operating procedure, SOP-CPK-0001, and the guidance document, GUI-CPK-3001, for more information regarding the treatment of plasma concentrations below the assay's lower limit of quantification (NQ). For this study, when there is

PWH115760

more than one embedded NQ, NQ will be treated as zero rather than missing or truncated. Leading and tailing NQ will be treated per SOP.

Individual plasma concentration-time profiles and median/mean profiles by treatment group will be plotted. Each of the figures will contain one plot on the untransformed scale (i.e. a linear plot) and one plot on the log transformed scale (i.e. log-linear plot).

Plasma drug concentrations excluded from the PK analysis (i.e. PK parameter calculation) will be excluded from the summaries and figures. These concentrations will be flagged in the listing of PK concentration data.

11.2. Deriving and Summarizing Pharmacokinetic Parameters

For subjects in each active treatment group the following pharmacokinetic parameters will be determined from the plasma concentration-time data for GSK1278863 and its metabolites [M2, M3, M4, M5, M6 and M13]. The pharmacokinetic parameters will be calculated by standard non-compartmental analysis according to current working practices and using WinNonlin Version 5.2 or higher. All calculations of non-compartmental parameters will be based on actual sampling times.

1. The first occurrence of the maximum observed plasma concentration determined directly from the raw concentration-time data (C_{max}).
2. The time at which C_{max} is observed will be determined directly from the raw concentration-time data (t_{max}).
3. The area under the plasma concentration-time curve to the last quantifiable concentration (AUC(0-t)), will be determined using the linear trapezoidal rule for increasing concentrations and the logarithmic trapezoidal rule for decreasing concentrations.
4. The AUC extrapolated to infinity (AUC_(0-∞)) will be calculated, where data permit, as the sum of AUC_(0-t) and C_{t/z}, where C_t is the observed plasma concentration obtained from the log-linear regression analysis of the last quantifiable time-point and z is the terminal phase rate constant. The percentage of the AUC_(0-∞) that is extrapolated will be calculated as the ratio of [AUC_(0-∞) minus AUC_(0-t)] to AUC_(0-∞).
5. The apparent terminal elimination half-life (t_{1/2}) obtained as the ratio of ln2/λz, where λz is the terminal elimination phase rate constant estimated by linear regression analysis of the log transformed concentration-time data (if data permits)
6. Trough concentration (C_τ) will be measured as the lowest concentration prior to dosing on Day 18 in Part B. Summary statistics of trough concentration will be used as an informal assessment of the attainment of steady state.

PWH115760

7. If data permit, the metabolite:parent AUC and Cmax ratios (corrected for molecular weight) will be calculated.

Time profile for PK concentration for individual subjects will be plotted by dose regimen and study day. Mean (SD) plot for PK concentration will be generated by dose regimen and day.

Pharmacokinetic data will be presented in graphical and/or tabular form and will be summarized descriptively. All pharmacokinetic data will be stored in the Archives, GlaxoSmithKline Pharmaceuticals, R&D. Statistical analyses of the pharmacokinetic parameter data will be the responsibility of Clinical Statistics, Quantitative Science, GlaxoSmithKline.

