- Instead of change from baseline, descriptive summaries will be created for the angiogenesis and blood flow and oxygen availability, the biomarkers in the DFU, the bioburden in the DFU, and biomarkers of systemic HIF activation in the blood.
- The only physical parameter to be evaluated is change in wound volume and area
- Correlation between GSK1278863 and PD and safety will not investigated further, unless multiple safety issues make is necessary

[figure not shown]
Given the time it takes to process the assay, the histology data will not be available for inclusion in the final data base at the time of database freeze. Therefore, this data will be analysed when it becomes available. If the results are available before CSR, then they will be included in the study report; otherwise, they will be included in an addendum to the study report or separate study report.

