8.6.3. Derived parameters for EPO

Cmax, tmax and AUC of EPO concentration will be derived for each subject by the study day (Part A: Day 1; Part B: Day 1, Day 8, Day14 or Day21).

The maximum observed concentration (Cmax) and the first time of its occurrence (tmax) will be obtained directly from the EPO concentration-time data for each subject by study day.

AUC will be calculated using linear trapezoidal rules. Let C1 and C2 be two adjacent concentration point and T1 and T2 be corresponding two adjacent time points, then according to the trapezoidal rule, the partial AUC between T1 and T2, $AUC[T1, T2] = (C1+C2)*(T2-T1)/2$, and total AUC is the sum of all partial AUC's within the defined time window.

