12. PHARMACODYNAMIC AND BIOMARKERS ANALYSES

12.1. Pharmacodynamic Analyses for DFU

12.1.1. Physical parameters of the wound

Wound volume/area, after log-e transformation if appropriate, will be analyzed using a repeat measures ANOVA model, fitting terms for regimen, visit, interaction of regimen and visit, and with compound symmetry variance-covariance structure, for Part B as data permit. The repeat measures ANOVA model will be used to produce least squares means, point estimates, and 95% confidence intervals for each post-dose time point vs Day 1 predose, , each post-repeat-dose time point vs Day 8 predose, as well as for the baseline corrected active versus placebo and active vs standard care (Part B) for each post-dose visiting time point(see Exhibit A)

Physical parameters of the wound will be summarized (for continuous measures) or tabulated (for categorical measures) by regimen and visit for Part A and Part B respectively. Descriptive summary stats include n, arithmetic mean and corresponding 95% confidence interval, standard deviation, minimum, median, maximum.

Mean (SE) plots will be produced by regimen, including part A and part B across study day (day 1, day 4 and follow-up for part A, Day 1 and Day 8 for part B), as well as for Part B alone, by regimen and study days (Exhibit H)

Physical parameters of the wound will be analyzed and summarized separately by methods (Acetate or photo).

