12.2.5. Circulating biomarkers of systemic HIF activation

Summary descriptive statistics and mean SE plot by regimen and visit will be produced (see Section 12.2.1).

CONFIDENTIAL

CM2009/00071/00

PWH115760

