14.1.3. Pharmacokinetic Figures and Tables

Tables

Table No.	Population	IDSL No. / Example Shell	Title	Programming Notes	Deliverable Priority
11.xx	PK	PKCT1	Summary of {Matrix} GSK1278863 Pharmacokinetic Concentration-Time Data	By treatment and visit time	SAC, in stream
11.xx	PK	PKCF6	Individual Subject Plasma GSK1278863A Concentration-Time Plots – by Treatment Regimen	1. X-axis displays actual relative time. 2. Include line for LLQ along with footnote defining LLQ value.	SAC

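### Three places in the SAP keep a superseded Part B calendar and conflict with the current visit schedule, and the accumulation ratio has no derivation

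*SAP*

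**What the plan says.** **Trough.** SAP 11.2 item 6: the Part B trough "will be measured as the lowest concentration prior to dosing on Day 18 in Part B", and its summary is to serve as an informal check that steady state was reached.

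**EPO.** SAP 8.6.3 derives EPO Cmax, tmax and AUC by study day, listing "Part B: Day 1, Day 8, Day14 or Day21".

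**Wound size.** SAP 12.1.1 contrasts each visit with Day 1 pre-dose, and adds "each post-repeat-dose time point vs Day 8 predose". A combined plot for both parts uses "Day 1 and Day 8 for part B".

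**Accumulation.** The ratio is among the repeat-dose PK parameters in SAP 2.2.1 and protocol 3.1, and protocol 6.3.2.2 repeats it, each time on condition that the data allow. SAP 11.2 does not define it. SAP 8.5 lists the baseline for PK parameters as Day 1.

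**Current Part B schedule** (protocol 4.2.2, 4.2.2.3, 4.6.2, 4.6.3):
- Dosing in clinic on Days 1, 4, 7 and 14; at home on Days 2-3, 5-6 and 8-13.
- PK on Days 1 and 7 at pre-dose and 2 h; on Day 14 at pre-dose, 1, 2, 4, 8, 10-12 and 24 h.
- EPO once, at pre-dose or the equivalent time, on Days 1, 7 and 15.
- Wound measurement on Days 1, 4, 7 and 15 and at the follow-up 7 to 10 days after the last dose.

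Protocol 1.4.1.3 still promises a Day 11 trough. Section 4.2.2 does not list that day, the trough row in 4.6.2 has no mark, and 4.6.3 has no Day 11 line.

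**The concern.** Amendment 6 removed the Part B single dose and the washout week that followed. Repeat dosing, which had started on Day 8, now starts on Day 1. The SAP's revision table records that redesign and two text revisions in 2017, yet these rules still name days from the longer calendar.

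This is operative analysis text, not change-log text. A programmer following it would find no trough data, could not form a Part B EPO profile, and would have no Day 8 wound value. The replacements would be chosen after the data are in hand, although SAP Section 1 says all final-analysis decisions were made before database freeze. The accumulation ratio raises a related question: with Day 1 as the only reference the SAP names, and one post-dose sample that day, it is unclear what would be divided by what.

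**Working it through.** **Dosing calendar.** Clinic days 4, plus home days 2 + 2 + 6 = 10, gives 14 dosing days ending on Day 14. This reproduces the stated 14-day period. Day 18 is 18 − 14 = 4 days after the last dose.

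**Each named day against the current schedule.** The old start of repeat dosing was Day 8 and the new one is Day 1, so the last columns test whether subtracting 8 − 1 = 7 days repairs the rule.

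| SAP rule | Days named | Current schedule on those days | Days minus 7 | Current schedule there |
|---|---|---|---|---|
| Trough, 11.2 item 6 | 18 | no dose, visit or PK sample | 11 | home dosing; no visit or PK sample |
| EPO, 8.6.3 (Part B) | 1, 8, 14, 21 | 1, 0, 0, 0 EPO samples | 8→1, 14→7, 21→14 | 1, 1, 0 EPO samples |
| Wound, 12.1.1 | 8 | home dosing; no measurement | 1 | measured, but repeats the Day 1 contrast |

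Renumbering therefore does not repair any of the three. Day 21 needs one qualification: the first follow-up falls on Days 14 + 7 = 21 to 14 + 10 = 24, so a wound measurement can land on Day 21. No EPO sample is scheduled at that visit.

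**What can still be run.** Part A EPO on Day 1 is sampled at pre-dose, 8 h and 10-12 h (protocol 4.6.1), so the Part A portion of 8.6.3 works. In 12.1.1 the contrasts against Day 1, the active-versus-control contrasts and the Part B-only plot all work. They agree with Exhibit A, which uses Day 7, Day 15 and follow-up, each against Day 1.

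**Accumulation.** On the current schedule, Day 1 AUC(0-t) covers at most 2 h and Day 14 AUC(0-t) up to 24 h. The intervals differ by 24/2 = 12 times, so the two AUCs are not comparable whatever the kinetics. With one post-dose sample, Day 1 Cmax can only be the 2 h value, and half-life and AUC(0-∞) cannot be estimated.

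**A possible outside comparator.** SAP Section 7 gives regimens E (single dose) and R1r (repeat dose) the same strength and amount, 1% at 100 mg/cm². E goes on the wound in period 1 of the final Part A cohort (protocol 4.2.1.5) and is sampled to 72 h. It shares six nominal post-dose times with R1r Day 14: 1, 2, 4, 8, 10-12 and 24 h. For scale, with the planned 6 and 12 active subjects and groups assumed independent, the 95% CI factor for a ratio is exp(t(0.975, 16 df) × SD × √(1/6 + 1/12)) = exp(2.12 × SD × 0.5). That is about 1.7 either way at an assumed log-scale SD of 0.5, and 2.9 at 1.0. Neither SD is in the documents.

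**Displays.** SAP 14.1.3 lists PK concentrations only: a summary and "Individual Subject Plasma GSK1278863A Concentration-Time Plots". The EPO displays in 14.1.2 are a raw summary and a time course. None of these, nor the Exhibit A wound table, needs a trough, an EPO profile or a Day 8 value.

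**The case against.** **The reporting is already settled.** SAP 2.2.2 restricts several endpoints to descriptive summaries, including "the bioburden in the DFU, and biomarkers of systemic HIF activation in the blood", and 12.2.5 adds "Summary descriptive statistics and mean SE plot by regimen and visit will be produced". Exhibit A uses the right days, and SAP 8.1 says changes from the plan will be stated in the study report. This stands, and it is why the point is minor. It does not clear the text: SAP Section 11 still says summary statistics "will be calculated for each derived plasma pharmacokinetic (PK) parameter by regimen and time", and 11.2 gives the trough a job that Day 18 cannot do.

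**The sample counts may not describe the data.** The Amendment 7 rationale says some Part B changes took place in stream without an amendment. The schedule it replaced had more Day 1 PK times, a Day 11 trough and EPO at three times on one day. Subjects sampled earlier may have those data; the documents do not say how many. This stands. The counts above describe the current schedule only, and a blanket ban on Part B Day 1 denominators or EPO profiles could discard usable samples.

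**Accumulation is conditional.** This also stands: the ratio may be dropped. But permission to omit it does not define it.

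**Stronger readings the documents do not support.** A reader might infer that all three rules return nothing; only the trough rule fails whole. A reader might infer that the SAP plans to divide a 24 h AUC by a 2 h AUC; no section proposes that ratio, so a simulated bias for it would not measure an error in the plan. A reader might treat E against R1r as a validated substitute; protocol 1.4.1.4 expects the PK to change during repeat dosing, subjects may take part in both parts, and the amount applied follows wound size.

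**Conclusion.** The conflict is real and minor. On the current schedule:
- the Day 18 trough rule returns no data;
- the Part B portion of the EPO rule cannot be derived;
- the Day 8 wound contrasts and plot point have no measurement;
- the accumulation ratio has no derivation, and Day 1 AUC(0-t) does not cover the same interval as Day 14.

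The calendar findings rest on the schedule in protocol 4.6.2 and 4.6.3 and need no assumption beyond it. They do not extend to subjects sampled under an earlier schedule. No listed display changes. The Amendment 7 rationale reports concentrations at 1%, 100 mg/cm² below the 0.10 ng/mL assay limit, without naming the study part. If that persists, accumulation will not be estimable by any route.

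**What to change.** - **SAP 11.2 item 6:** define trough as pre-dose Day 7, pre-dose Day 14 and the 24 h sample after the Day 14 dose, plus pre-dose Day 11 where it was collected under the earlier schedule. Report counts below the quantification limit.
- **SAP 8.6.3:** limit EPO Cmax, tmax and AUC to Part A Day 1. Summarise Part B EPO on Days 1, 7 and 15, and list any additional timed samples.
- **SAP 12.1.1:** delete the Day 8 contrasts and plot the measured visits (Days 1, 4, 7, 15 and follow-up).
- **SAP 8.5 and 11.2:** state that AUC or Cmax from a Part B Day 1 profile with only a 2 h post-dose sample will not be an accumulation denominator. Where a fuller Day 1 profile exists, compare the same interval on Days 1 and 14. Otherwise report accumulation as not estimable, or show R1r Day 14 AUC(0-24 h) against regimen E (wound application) AUC(0-24 h) descriptively, with the amount applied from SAP 8.6.6. Note the possible overlap of subjects, differing wound sizes and PK that may change over time.
- **Protocol 1.4.1.3:** reconcile the Day 11 trough with 4.2.2, 4.6.2 and 4.6.3.

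The cost is text only: no new samples, visits or displays. The between-part comparison would be imprecise, and it disappears if concentrations stay below the assay limit.

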12. PHARMACODYNAMIC AND BIOMARKERS ANALYSES

12.1. Pharmacodynamic Analyses for DFU

12.1.1. Physical parameters of the wound

Wound volume/area, after log-e transformation if appropriate, will be analyzed using a repeat measures ANOVA model, fitting terms for regimen, visit, interaction of regimen and visit, and with compound symmetry variance-covariance structure, for Part B as data permit. The repeat measures ANOVA model will be used to produce least squares means, point estimates, and 95% confidence intervals for each post-dose time point vs Day 1 predose, , each post-repeat-dose time point vs Day 8 predose, as well as for the baseline corrected active versus placebo and active vs standard care (Part B) for each post-dose visiting time point(see Exhibit A)

Physical parameters of the wound will be summarized (for continuous measures) or tabulated (for categorical measures) by regimen and visit for Part A and Part B respectively. Descriptive summary stats include n, arithmetic mean and corresponding 95% confidence interval, standard deviation, minimum, median, maximum.

Mean (SE) plots will be produced by regimen, including part A and part B across study day (day 1, day 4 and follow-up for part A, Day 1 and Day 8 for part B), as well as for Part B alone, by regimen and study days (Exhibit H)

Physical parameters of the wound will be analyzed and summarized separately by methods (Acetate or photo).

12.1.2. Clinical parameters of the wound

Clinical parameters of the wound will be summarized (for continuous measures) or tabulated (for categorical measures) by regimen and visit for Part A and Part B respectively. Descriptive summary stats include n, arithmetic mean and corresponding 95% confidence interval, standard deviation, minimum, median, maximum. Tabulation for categorical endpoints will be presented in a frequency table (n, % by regimen and visiting time).

Similar ANCOVA model as 12.1.1, as well as Mean (SE) plot, may apply to (continuous) clinical parameters of the wound as data permit.

12.2. Biomarker Analyses

12.2.1. Wound fluid biomarkers: Cytokines

Change from baseline wound fluid biomarkers, including cytokines, growth factors and proteases, after log-e transformation if appropriate (i.e. change from baseline becomes log ratio on the loge transformed data), will be analyzed separately for Part A DFU and Part B.

Descriptive statistics (n, arithmetic mean and corresponding 95% confidence interval, standard deviation, minimum, median, maximum) will be calculated by regimen and visiting time points. In addition, in cases that loge transformed data are used in the analysis, geometric means (and corresponding 95% confidence interval) and between subject coefficients of variation (CVb) will be calculated by regimen and visit time points, where Geometric mean = $\exp(\text{mean on loge-scale})$ CVb(%) = $\sqrt{\exp(\text{sd2}) - 1} \times 100$ where sd is the standard deviation of the loge-transformed data.

Mean (SE) plots will be produced by regimen agent across visit.

12.2.2. Wound fluid biomarkers: Bioburden

Similar summary descriptive statistics and mean SE plot by regimen and visit will be produced (see Section 12.2.1).

12.2.3. Gene expression in the DFU tissue

The qPCR data from the forsyth vendor will be analysed by target science and the finding will be summarized in a separate report.

12.2.4. Biomarkers of angiogenesis and blood flow and oxygen

Similar summary descriptive statistics and mean SE plot by regimen and visit will be produced (see Section 12.2.1).

CONFIDENTIAL

CM2009/00071/00

PWH115760

12.2.5. Circulating biomarkers of systemic HIF activation

Summary descriptive statistics and mean SE plot by regimen and visit will be produced (see Section 12.2.1).

CONFIDENTIAL

CM2009/00071/00

PWH115760

13. REFERENCES

14. ATTACHMENTS

14.1. Table of Contents for Data Display Specifications

14.1.1. Study Population

Table No.	Population	IDSL No. / Example Shell	Title	Additional Programming Notes	Deliverable Priority
1.01	All Subjects	DM1	Summary of Demographic Characteristics		SAC, in stream
1.02	Enrolled	DM11	Summary of Age Ranges		
1.03	All Subjects	IE1	Summary of Inclusion/Exclusion Criteria Deviations		SAC
1.04	All Subjects	DM5	Summary of Race and Racial Combinations		SAC
1.05	All Subjects	ES1	Summary of Subject Disposition		SAC, in stream
1.06	All Subjects	ES6	Summary of Reasons for Run-In Failure		SAC, in stream
1.07	Enrolled	NS1	Summary of Number of Subjects by Country and Site ID		SAC

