4.2.1.3. Run-In Period (Part A)

For two weeks prior to Day 1 of the DFU Treatment Period, subjects will receive standard-of-care. For all diabetic subjects in Part A, each subject's DFU will be measured at screening and Day 1; if, after 14 (± 1 day) days from screening, the subject's DFU has reduced in size by greater than 30 %, the subject will not be randomized to receive investigational product. If Screening and Day 1 are not 14 days (± 1 day) apart, an additional visit (Optional Baseline Run-In) will need to be scheduled prior to Day 1 to meet the Run-In requirement. Subjects that do not meet randomization eligibility will be discontinued from the study.

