4.2.2.2. Run-In Period (Part B)

For two weeks prior to Day 1 of the Treatment Period, subjects will receive standard-of-care as described in Section 7.4. For all subjects in Part B, each subject's DFU will be measured at screening and Day 1; if, after 14 days from screening, the subject's DFU has reduced in size by greater than 30 %, the subject will not be randomized to receive investigational product and is considered a Run In Failure. If Screening and Day 1 are not 14 days (± 1 day) apart, an additional visit (Optional Baseline Run In) will need to be scheduled prior to Day 1 to meet the Run In requirement. Subjects that do not meet randomization eligibility will be discontinued from the study.

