5.4. Screen and Baseline Failures

Data for screen and baseline failures will be collected in source documentation at the site but will not be transmitted to GSK.

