5. ANALYSIS POPULATIONS

All Subject Population: All subjects who receive at least one dose of study drug (including GSK1278863, placebo and standard care) will be included in the All Subject Population. Randomized subjects will only be excluded if there is clear documented evidence of failure to take any study medication. Subjects in the All Subject Population will be analyzed according to the treatment received and will be used for the reporting of safety and study population.

Enrolled: All participants who sign informed consent and for whom a record exists on the study database. This population will be used for the tables/listings of reasons for withdrawal before randomization and listings of AEs and SAEs for non-randomized participants.

Pharmacodynamic (PD) Population: All subjects who provide pharmacodynamic (PD) data will be included in the PD population. This population will be used in the evaluation of PD. For the change from baseline assessment, only those providing both evaluable baseline and post-dose values (so that the change can be calculated) will be included in the analysis. All subjects in the PD Population will be analyzed according to the treatment they actually received.

Pharmacokinetic (PK) Population: All subjects from whom a pharmacokinetic (PK) sample has been obtained and analyzed will be included in the PK population. This population will be used for reporting of PK concentration and the PK parameters.

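### SAP Table 1.06 summarises run-in failures in a population of dosed subjects, so first-time entrants who fail run-in cannot appear in it

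*SAP*

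**What the plan says.** **SAP Section 14.1.1** lists Table 1.06, "Summary of Reasons for Run-In Failure", with All Subjects in the population column.

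**SAP Section 5** defines that population as "All subjects who receive at least one dose of study drug", and names active drug, placebo and standard care as study drug. It then says "Randomized subjects will only be excluded if there is clear documented evidence of failure to take any study medication".

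**SAP Section 5** defines the Enrolled population as "All participants who sign informed consent and for whom a record exists on the study database" and gives its purpose: "This population will be used for the tables/listings of reasons for withdrawal before randomization".

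**SAP Section 14.1.5** assigns Listing 20, the subject-level listing of run-in failure reasons, to Enrolled.

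**Protocol Section 4.2.2.2 (Part B)** says that if the ulcer shrinks by more than 30% during run-in, "the subject will not be randomized to receive investigational product and is considered a Run In Failure". **Protocol Section 4.2.1.3 (Part A)** applies the same threshold and adds: "Subjects that do not meet randomization eligibility will be discontinued from the study".

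**Protocol Section 5.4** says: "Data for screen and baseline failures will be collected in source documentation at the site but will not be transmitted to GSK".

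**The concern.** A table of run-in failures needs a population that can contain run-in failures. All Subjects is defined by dosing. Run-in failure is decided before randomization, and so before dosing. For anyone entering the study for the first time, the two conditions exclude each other.

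Table 1.06 is the only planned summary table of why subjects were lost at run-in. Subject disposition (Table 1.05) is also on All Subjects, so it does not fill the gap. If Table 1.06 is produced as specified and comes out empty, a reader of the study report could conclude that nobody failed run-in. The run-in removes ulcers that shrink quickly under standard care, so this attrition helps to describe the ulcers to which the exploratory wound results apply.

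There is a second gap. The SAP expects database records for people who were never randomized, while Protocol Section 5.4 keeps at least some failure data at the site. Changing the population may not be enough to fill the table.

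**Working it through.** The plan states no figure here, so there is nothing numerical to reproduce. The check compares the definitions.

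**1. Who is in All Subjects?** Subjects with at least one dose of an assigned treatment (SAP Section 5).

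**2. Who is a run-in failure?** A subject whose ulcer area falls by more than 30% over the two-week run-in, and who is then not randomized (Protocol Sections 4.2.1.3 and 4.2.2.2).

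**3. Overlap for first-time entrants.** Not randomized means no assigned treatment, so no dose. The overlap of (dosed) and (run-in failure) is 0 subjects.

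**4. Overlap for re-entrants.** Protocol Section 4.2.1 lets diabetic subjects join more than one Part A cohort and go on to Part B, with healing rate checked again each time. SAP Section 8.1 reports such subjects under the number from their first entry. A subject dosed in one cohort who fails a later run-in is therefore already in All Subjects and could be counted. A Cohort 2 subject dosed on intact skin in Period 1 (Protocol Section 4.2.1.4) might be in the same position.

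**5. What each population would show.** Let *F* be the run-in failures with a database record, and *R* those among them who had been dosed earlier.

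| Population for Table 1.06 | Failures shown |
|---|---|
| All Subjects (as specified) | *R* |
| Enrolled | *F* |
| Shortfall as specified | *F* − *R* |

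The documents give neither *F* nor *R*. If no failure had been dosed earlier, *R* = 0 and the table omits all *F*. If some had, it shows only those.

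**6. Does the SAP agree with itself?** No. Section 5 sends this content to Enrolled, in tables as well as listings. Listing 20 follows that rule and Table 1.06 does not. The listing could show *F* subjects while its own summary shows *R*. SAP Section 9 makes All Subjects the default for study population tables unless otherwise specified, which may explain the entry, but Section 5 does specify otherwise for this content.

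**7. Would the data be there?** Protocol Section 5.4 covers screen and baseline failures and does not name run-in failures. Including them is a natural reading, because the run-in decision is made at or just before Day 1 and the extra visit is called the Optional Baseline Run-In. If they are included, *F* = 0 on the sponsor's database in any population. The SAP's Enrolled definition and Listing 20 assume the opposite. The documents do not settle which holds.

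**The case against.** The strongest reply is that this is one wrong cell in a table of contents. Listing 20 already gives each failure's reason on the right population, no hypothesis is tested, the primary endpoints are safety and PK, and the wound results are exploratory. All of that stands and limits the weight of the point. It does not make the table right.

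Four stronger readings might be inferred, and the documents do not support them:

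- **That the table must show zero whatever the true number.** Earlier-dosed subjects who fail a later run-in could appear.
- **That the protocol says run-in failure data never reach the sponsor.** Section 5.4 does not mention run-in failures. Other provisions point to some information leaving the site: sponsor-supplied subject numbers are assigned at screening (4.3.1), all wound tracings go to the core lab (7.9.2.2), and SAEs related to study participation are recorded from consent (Section 12).
- **That standard care given during run-in counts as a dose, bringing every run-in failure into the safety denominator.** SAP Section 3 treats standard care as an assigned Part B treatment, Section 7 gives it a randomization code, and the next sentence of the All Subjects definition speaks of randomized subjects. This reading would also fill Table 1.06, so it cannot be held together with an empty one.
- **That the disposition tables as a group are wrong.** Only Table 1.06 is shown to be on a population that conflicts with its content.

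**Conclusion.** The point holds for Table 1.06. Its population conflicts with the SAP's own rule for pre-randomization withdrawals and with Listing 20. As specified, the table omits every first-time entrant who fails run-in and can count only subjects dosed earlier in the study. This rests on reading standard care in the All Subjects definition as the randomized arm, which is the reading the SAP supports.

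The size in subjects is unknown, because the documents report no run-in failures. The consequence is a misleading attrition summary. No safety, PK or wound estimate changes.

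Whether the data exist on the sponsor's database is a separate open question. The protocol is silent on run-in failures in Section 5.4, and the SAP assumes that records are available.

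**What to change.** 1. In SAP Section 14.1.1, change the Table 1.06 population from All Subjects to Enrolled, to match Section 5 and Listing 20. Cost: one cell and the matching program setting.

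2. Reconcile Protocol Section 5.4 with the SAP by stating whether run-in failures fall under its data rule, and whether their reasons are on the study database. Cost: a check of the database and a sentence in the SAP.

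3. If no run-in failure data were transmitted, either drop Table 1.06 and Listing 20 or footnote both to say that the data were not collected by the sponsor. Cost: one footnote or two deletions.

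New eCRF fields are not proposed. The SAP's last revisions date from September and October 2017, after the indication was terminated and outputs had been cut back, so new data collection at that stage would not clearly be cheap.
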